END OF STUDY AND LENGTH OF STUDY

The end of this study is defined as the date when the last patient, last visit (LPLV), occurs or the date at which the last data point required for statistical analysis or safety follow-up is received from the last patient, whichever occurs later. The end of the study is expected to occur 48 months/4 years after the last patient is enrolled.

In addition, the Sponsor and/or Collaborator (Genentech) may decide to terminate the study at any time.

The total length of the study, from screening of the first patient to the end of the study, is expected to be approximately 6–7 years.

RATIONALE FOR STUDY DESIGN

Rationale for Ocrelizumab Dose and Schedule

Consistent with the USPI, the ocrelizumab dose administered in this study is 600 mg every 24 weeks. Three-courses of ocrelizumab or placebo will be administered over the course of the study. The first dose of ocrelizumab will be administered as two 300 mg IV infusions on Week 0 (Day 1) and Week 2 (Day 15), with the subsequent second- and third-courses given as a single 600 mg infusion at Weeks 24 and 48. Study drug for patients randomized to the placebo group will be administered analogously to those receiving ocrelizumab. Patients will then be followed in the clinical trial for 3 years.

Administering three-courses of ocrelizumab permits the interrogation of the immunodynamics surrounding the emergence of CNS autoimmunity and the reconstitution of the immune system following anti-CD20 B cell depletion with ocrelizumab. Understanding the effect of B cell depletion in RIS using this treatment paradigm will provide invaluable insight into the onset of MS, as well as the mechanism of action of ocrelizumab, both of which remain poorly understood.

Rationale for Patient Population and Use of 2017 McDonald Criteria

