Treatment may be stopped at any time due to lack of clinical benefit, unacceptable toxicity, withdrawal of consent, patient or physician decision to discontinue treatment, death, or if the sponsor decides to close the trial, whichever occurs first.

Treatment of Radiologic Event

In the event of radiologic progression, in which a new contrast-enhancing or T2-weighted lesion suggestive of MS develops, the choice to continue or discontinue from the study

in order to initiate treatment with a DMT, including commercial OCREVUS®, is at the discretion of the treating physician. If a commercial disease modifying therapy is initiated, the participant will be discontinued from all study-related treatments.

Regardless of whether the participant is started on commercial disease modifying therapy, individuals with a radiologic event should complete study assessments until they have completed week 208 or until they have had a confirmed clinical relapse, whichever occurs first.

As described above in Section 4.4.1 treatment may be stopped at any time due to lack of clinical benefit, unacceptable toxicity, withdrawal of consent, patient or physician decision to discontinue treatment, death, or if the sponsor decides to close the trial, whichever occurs first.

Prohibited Therapy

The following therapies for MS are not permitted during the treatment portion of the study (through week 72): Other B-cell targeted therapies (e.g., rituximab, atacicept, belimumab, or ofatumumab, etc.), natalizumab, fingolimod, siponimod, alemtuzumab, daclizumab, cladribine, teriflunomide, dimethyl fumarate, diroximel fumarate, ozanimod, interferons, glatiramer acetate, cyclophosphamide, mitoxantrone, azathioprine, mycophenolate mofetil, cyclosporine, methotrexate, total body irradiation, bone marrow transplantation, IV Ig, plasmapheresis, other approved or investigational therapies for MS.

After patients have completed (or discontinued) treatment with study drug, they may receive alternative treatment for MS as judged clinically appropriate by the investigator. However, as sufficient data are not available regarding risks associated with switching to other products, the following recommendations are given:

Caution is advised if patients remain B-cell depleted.

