When a patient withdraws from the study, samples collected prior to the date of withdrawal may still be analyzed, unless the patient specifically requests that the samples be destroyed or local laws require destruction of the samples. However, if samples have been tested prior to withdrawal, results from those tests will remain as part of the overall research data.

Data arising from sample analysis will be subject to the confidentiality standards described in Section 4.5.19.2 and Section 8.4.

Hepatitis Screening and Liver Function Monitoring

Patients with recurrent or chronic hepatitis B or history/presence of hepatitis C infection must be excluded from enrollment into the study. Hepatitis B and C serology will be performed at screening.

A positive result to either HBsAg, total HBcAb associated with positive viral DNA titers as measured by PCR, or a positive result for HepCAb should result in the patient's exclusion.

Patients with evidence of past resolved hepatitis B infection (i.e., positive total HBcAb associated with a negative viral DNA) can be enrolled and will have the hepatitis B viral DNA checked regularly as per the schedule of activities (see Appendix 1).

Patients in whom the viral DNA becomes positive but in whom the quantity is at the lower limit of detection of the assay should have the test repeated as soon as possible. Patients found to have a confirmed viral DNA-positive test should be referred to a hepatologist for immediate assessment. These patients will not receive further ocrelizumab infusions.

Liver function (i.e., ALT, AST, alkaline phosphatase, and total bilirubin) should be reviewed throughout the study. Patients developing evidence of liver dysfunction should be assessed and, if necessary, referred to a hepatologist or other appropriately qualified expert. Study drug should be withheld until the diagnosis of viral hepatitis has been excluded.

Patients developing hepatitis B or C should be withdrawn from the study. Should treatment be prescribed, this will be recorded on the eCRF. Patients with viral hepatitis due to other agents, such as hepatitis A, may resume treatment after the patient's recovery.

Patient-Reported Outcomes

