Complete physical examination ^h		x	x	x	x	x	x	x	x	x	x	x	x	x
EDSS		x	x		x	x	x	x	x	x	x	x	x	x
Neurologic examination ⁱ		x	x	x	x	x	x	x	x	x	x	x	x	x
Prescreen MRI	x ^w													
MRI brain ^{p,q}		x			x	x	x	x		x		x	x ^r	x ^r
MRI C-spine ^{p,q}		x			x	x	x	x		x		x	x ^r	x ^r
Symbol Digit Modality test for cognition	x*		x		x	x	x	x	x	x	x	x	x	x
Neuro QoL	x*		x		x	x	x	x	x	x	x	x	x	x
Assessment of neurologic event			x	x	x	x	x	x	x	x	x	x	x	x
Hematology, chemistry, and urinalysis ^j (Local lab)		x	x	x	x	x		x		x	x	x	x	x
Pregnancy test ^k		x	x	x	x	x								x
Hepatitis screening		x												
Hepatitis B virus DNA test ^l		x												

	Pre-screening (family members)	Screening ^a	Double-Blind Phase ^v											Unscheduled Visit ^b	Study Completion/ Early Termination ^c
Week	-6	-6	0 Baseline	2	24	48	72	104	130	156	182	208			
Visit Windows (days)	-45-1	-45-1	(-28)	(± 7)	(± 7)	(± 7)	(± 7)	(± 7)	(± 7)	(± 7)	(± 7)	(± 7)			
Quantitative Ig (total Ig, IgG, IgM, and IgA) (local lab)		x													
Quantitative Ig (total Ig, IgG, IgM, and IgA) (central lab)			x ^x		x	x	x	x	x	x	x	x	x	x	x
Lumbar puncture/CSF analysis (local lab and biomarkers) ^{m,p,s}			x ^x					x					x	x ^t	x ^r
Peripheral blood sample for biomarkers ^{m,s,t}	x		x ^x		x	x	x	x	x	x	x	x	x	x	x
Peripheral blood sample, paired with CSF			x ^y					x ^y				x ^y	x ^y	x ^y	
Serum samples for biomarkers ^{m,s}	x		x ^x		x	x	x	x	x	x	x	x	x	x	x
Gingival swab for storage	x [*]		x ^x		x	x	x	x	x	x	x	x	x	x	x
Adverse events ^u		x	x	x	x	x	x	x	x	x	x	x	x	x	x
Concomitant medications review		x	x	x	x	x	x	x	x	x	x	x	x	x	x
Randomization IxRS		x													
Methylprednisolone and antihistamine premedication ⁿ			x	x	x	x									
Ocrelizumab or placebo administration ^o			x	x	x	x									

eCRF = electronic Case Report Form; EDSS = Expanded Disability Status Scale; HBcAb = hepatitis B core antibody; HBsAg = hepatitis B surface antigen; HBV = hepatitis B virus; HepCAb = hepatitis C; MRI = magnetic resonance imaging; MS = multiple sclerosis; NfL = neurofilament light; WGS=Whole genome sequencing; PBMC=peripheral blood mononuclear cells; CSF= cerebrospinal fluid.

Note: (x) indicates that an assessment will only be done if needed.

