ⁱ Neurological examinations will be used to distinguish a neurologic event suggestive of MS (i.e., CNS demyelination) from other neurological (non-MS) disorders. Potential neurologic events suggestive of CNS demyelination should be recorded throughout the study period. Investigators will also screen patients for signs and symptoms of worsening neurologic function localized to the cerebral cortex, such as cortical symptoms/signs, behavioral and neuropsychological alteration, retrochiasmal visual defects, hemiparesis, cerebellar symptoms/signs (e.g., gait abnormalities, limb incoordination). Patients with suspected PML should be withheld from ocrelizumab treatment until PML is ruled out by complete clinical evaluation and appropriate diagnostic testing. A patient with confirmed PML should be withdrawn from the study. PML should be reported as a serious adverse event (with all available information) with immediate notification of the Medical Monitor.

^j Hematology will include hemoglobin, hematocrit, RBCs, WBC absolute and differential, absolute neutrophil count, and quantitative platelet count. Chemistry will include AST, ALT, total bilirubin, urea or BUN, creatinine, potassium, sodium and calcium. Standard urinalysis will be used to assess kidney function. For those patients enrolled with negative HBsAg and positive total HBcAb, HBV DNA (PCR) must be repeated every 24 weeks during these timepoints.

^k Serum or urine β -hCG must be performed at screening in women of childbearing potential within 14 days prior to initiation of study drug. Subsequently, urine β -hCG (sensitivity \geq 25 mIU/mL) must be collected. On infusion visits, the urine pregnancy test should be performed prior to premedication in all women of childbearing potential. If positive, ocrelizumab should be withheld and pregnancy status confirmed with serum β -hCG test.

^l All patients must have negative HBsAg result and negative HepCAb screening tests prior to study enrollment. If HBcAb is positive at screening, HBV DNA measured by PCR must be negative. For those patients enrolled with negative HBsAg and positive total HBcAb, HBV DNA (PCR) must be repeated every 24 weeks during the treatment period.

^m Biomarkers assessed in peripheral blood, CSF, and serum include adaptive and innate immune cell subsets and their soluble factors, RNA, DNA, genetic risk factors (e.g. HLA-DRB1*15:0), and other emerging exploratory markers of disease biology as appropriate. If samples are

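### The two footnotes on repeat HBV DNA testing in core-antibody-positive patients share a 24-week interval but not an end date, so post-treatment monitoring is left undefined

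*Combined protocol and SAP*

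**What the plan says.** The section on Hepatitis Screening and Liver Function Monitoring says that patients with resolved past infection (core antibody positive, viral DNA negative) "can be enrolled and will have the hepatitis B viral DNA checked regularly as per the schedule of activities (see Appendix 1"). It gives no interval and no end, so Appendix 1 is the operative rule.

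Appendix 1 states the re-test rule twice for the same patients:

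- Footnote l, on the row "Hepatitis B virus DNA test": "HBV DNA (PCR) must be repeated every 24 weeks during the treatment period".
- Footnote j, on the row "Hematology, chemistry, and urinalysis": "HBV DNA (PCR) must be repeated every 24 weeks during these timepoints". The same footnote puts liver enzymes on that row: "Chemistry will include AST, ALT, total bilirubin".

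The HBV DNA row is marked at Screening and nowhere else.

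The protocol does not define the treatment period for this test. The Rationale for Ocrelizumab Dose and Schedule gives the last infusion at Week 48 and adds: "Patients will then be followed in the clinical trial for 3 years". The Prohibited Therapy section lists drugs "not permitted during the treatment portion of the study (through week 72"). The Blinding section uses the phrase more broadly, for the double-blind period.

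**The concern.** A site that enrols such a patient cannot tell from Appendix 1 when HBV DNA testing may stop. One footnote points to the dosing period and the other to a row that runs to Week 208.

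The difference matters after the last infusion, because B-cell depletion outlasts dosing. The section on Delayed Return of Peripheral B Cells gives a median repletion time of 72 weeks and asks that patients with prolonged depletion be monitored until repletion. CD19 counts are blinded, so sites cannot see for themselves when depletion has ended. A confirmed positive DNA result leads to urgent hepatology referral, but only if a test is done.

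**Working it through.** **Inputs.** Scheduled visits after Week 2 (Appendix 1): Weeks 24, 48, 72, 104, 130, 156, 182 and 208, each with a window of 7 days either side and timed from Day 1. Last infusion: Week 48. Repletion after the last infusion (51 Phase II patients): median 72 weeks, range 27 to 175.

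**Step 1: the footnote j row.** It is ticked at Screening, Weeks 0, 2, 24, 48, 104, 156, 182 and 208, unscheduled visits and completion. It is blank at Weeks 72 and 130. As a check on the column reading, the MRI rows read the same way give Screening and Weeks 24, 48, 72, 104, 156 and 208, which agrees with the contrast visits in footnote q (Screening, 48, 104, 156, 208).

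**Step 2: gaps between visits, in weeks.**

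| Visits used | Gaps from Week 0 (Week 2 omitted) |
|---|---|
| Footnote j row | 24, 24, 56, 52, 26, 26 |
| All scheduled visits | 24, 24, 24, 32, 26, 26, 26, 26 |

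On its own row, footnote j's interval fails straight after Week 48: 104 − 48 = 56 weeks, or 54 to 58 with windows. If every scheduled visit is used, it holds to Week 72. The next gap is then 104 − 72 = 32 weeks (30 to 34 with windows), followed by gaps of 26 weeks (24 to 28). A 26-week gap shrinks to 24 only if one visit is 7 days late and the next 7 days early, which cannot happen at successive gaps.

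**Step 3: strict 24-weekly due dates to Week 208.** These are Weeks 24, 48, 72, 96, 120, 144, 168 and 192, which is 8 tests. Weeks 24, 48 and 72 fall within a window of some scheduled visit. The other 5 fall within none. Only Weeks 24 and 48 match a ticked visit on the footnote j row.

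**Step 4: footnote l against B-cell return.** I assume that the Phase II repletion times apply after the Week 48 infusion.

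- Earliest: 48 + 27 = Week 75
- Median: 48 + 72 = Week 120
- Latest: 48 + 175 = Week 223

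| Footnote l ends at | Tests required | Weeks before earliest return | Weeks before median return |
|---|---|---|---|
| Week 48 | 2 | 75 − 48 = 27 | 120 − 48 = 72 |
| Week 72 | 3 | 75 − 72 = 3 | 120 − 72 = 48 |

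Under the Week 48 reading, the last required sample would normally precede the last infusion, because pre-infusion results are to be available before dosing. No required test would then follow that dose.

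**Step 5: liver enzymes.** ALT, AST and bilirubin sit on the footnote j row, so none is scheduled in the 56 weeks between Weeks 48 and 104.

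**The case against.** The strongest reply is that this is uncertainty about an end date and not a contradiction. That is right. Both footnotes name the same patients, test and interval, footnote l does not forbid later testing, and a site that draws every 24 weeks through the longer scope satisfies both.

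Four stronger readings are tempting, and the documents do not support them.

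- **That the protocol accepts a 56-week gap in HBV DNA testing.** It does not. Testing only at the ticked visits (6 tests) would breach footnote j's own 24-week requirement. The row invites that mistake but does not authorize it.
- **That the 24-week interval is unworkable in every case.** It fails only if testing continues past dosing. If footnote l governs and ends at Week 72, scheduled visits at Weeks 24, 48 and 72 meet it, although Week 72 has no local safety laboratory draw. Unscheduled visits are also allowed.
- **That footnote l itself runs to Week 208.** This is its weakest reading. The Immunizations section separates the treatment period from the time a patient stays depleted, and the exclusion criteria separate the treatment phase from the 6 months after the last infusion.
- **That testing until repletion is already required.** The request to monitor until repletion does not name HBV DNA.

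There are also real safeguards. The Infections section sends seropositive patients to liver experts before treatment, asks for monitoring to local standards, and reports no reactivation in ocrelizumab-treated MS patients in interventional studies (one in rheumatoid arthritis). Liver function is to be reviewed throughout the study. These lower the stakes, but they do not tell a site which footnote to follow, and review throughout is hard to meet where no chemistry is scheduled.

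One caution concerns the table. Its legend provides an (x) mark for assessments done only if needed, and I found none in the table text. If such a mark exists at later visits on the HBV DNA row, the remark about that row falls, but the difference between the footnotes remains.

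**Conclusion.** The point holds as a gap in post-treatment safety monitoring. The footnotes differ in scope, and no text fixes the end of testing. Under footnote l, required testing can end 3 to 27 weeks before the earliest expected B-cell return and 48 to 72 weeks before the median. Under footnote j, the required interval cannot be met at the row's own visits after Week 48.

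A reader might infer that re-dosing is unsafe. It is not affected: every reading tests at Weeks 24 and 48, the two re-dosing visits, and no study drug follows. No efficacy analysis is affected either.

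The subgroup's size is not given and is probably small. With 1:1 randomization, about half of it receives placebo. The timing figures rest on the Phase II repletion times carrying over to this population and to three courses of treatment. The difference in wording and the visit gaps need no such assumption. The protocol should be clarified, but the trial's conclusions do not depend on it.

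**What to change.** Replace the two re-test sentences with a single rule for patients enrolled with positive total HBcAb.

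- **Visits.** Mark the HBV DNA row conditionally at Weeks 24, 48, 72, 104, 130, 156, 182 and 208, where biomarker blood is already drawn.
- **End.** State it explicitly: Week 208, or an earlier end set by the sponsor's clinicians, such as B-cell repletion reported by the central laboratory in a way that preserves the blind. Week 208 would still fall 223 − 208 = 15 weeks short of the longest repletion time in Step 4.
- **Interval.** Keep 24 weeks as the target through Week 72, then test at every scheduled visit. Dropping the interval without comment would loosen a safety rule, so the 32-week gap from Week 72 to Week 104 needs a clinical decision. One added draw between Weeks 80 and 96 would keep both parts of it within 24 weeks. The later gaps would remain 26 weeks.
- **Liver enzymes.** Tick chemistry at Weeks 72 and 130, at least for these patients.

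**Cost per affected patient.** Eight PCR tests mean 8 − 2 = 6 more than footnote l to Week 48, 8 − 3 = 5 more than footnote l to Week 72, and none more than strict 24-weekly testing to Week 208. The optional draw adds one. There are also two chemistry panels. Because sites are blinded, placebo patients would be tested too. Apart from the optional draw, no visit is added.
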